There is now emerging evidence of efficacy of rTMS in the treatment of other psychiatric disorders such as panic disorder and anxiety (45-53). However, the utility of rTMS in the treatment of PTSD has not been extensively studied and only a limited number of studies exist with small sample sizes, and differing methodologies. PTSD can lead to abnormal changes in brain metabolism in certain cortical and subcortical areas. Two of the most frequent positron emission tomography (PET) and functional rTMS & PTSD Protocol V3.0 2 December 10, 2012

magnetic resonance imaging (fMRI) findings suggest decreased activity in the medial prefrontal cortex (mPFC) and the anterior cingulate cortex, while increased amygdala activation is commonly seen (54;55). These brain regions have reciprocal connections to DLPFC so by altering brain function in one accessible (to rTMS) region such as the DLPFC, it can indirectly lead to changes in other regions (56). Moreover, studies of those with PTSD have shown greater abnormality in the right hemisphere compared to left hemisphere, making the right side a more specific target for brain stimulation (57). These changes could theoretically lead to improvement in PTSD symptoms.

Preliminary uncontrolled studies suggest that rTMS has an effect on PTSD symptoms. Grisaru and colleagues treated 10 patients with *bilateral* rTMS using 0.3 Hz for 30 stimuli in a single session (58) while McCann et al. treated two patients for 10 sessions of 20 Hz rTMS over the *left* DLPFC (59). Both studies showed improvement in core PTSD symptoms, but the effects were transient. Rosenberg examined the effects of rTMS with *left* DLPFC at 1 Hz or 5 Hz in 12 patients with comorbid PTSD and MDD (60), and found large effects on depressive symptoms and smaller, but statistically significant, improvement in PTSD symptoms.

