The rTMS program at Vancouver General Hospital (VGH) currently focuses on the treatment of patients with depression. Patients typically receive 20-30 treatment sessions over a 4-6 week period. Sessions are conducted on consecutive days, five days a week, by a rTMS-clinic registered nurse under the supervision of a psychiatrist trained in rTMS. Each session lasts approximately 30 to 40 minutes. The clinic is currently situated right within Centennial Pavilion with ready access to emergency response teams and equipment in the unlikely event of a serious adverse reaction occurring during the treatment. The clinic is slated to move to Willow Pavilion in July 2012, which also has ready access to emergency response.

The Outpatient Psychiatry Program (OPP) PTSD program at the VGH Health Centre consists of a twophase, 18 week psycho-educational and behavioural skills program developed from the work of Ogden, Harris, and Najavits aimed at reducing symptoms of PTSD (65-67). Phase One is eight weeks long and includes psychoeducation about psychological trauma. Phase Two is 10 weeks long, and is designed to address longer term or complex traumatic stress disorders. The second phase is based on two models: Trauma, Recovery, and Empowerment (TREM) and Seeking Safety (66;67). Patients are referred from community care providers and are expected to complete the 18 week program if accepted. These patients are not combat veterans since there is already another existing resource for treating those patients elsewhere. Preliminary data from our clinic indicate that those patients completing Phase 1 of our program have very little improvement in their PTSD symptom scores, but Phase 2 can have a greater impact.

The presence of both programs at one site provides a unique opportunity to examine both the short and longer-term effects of rTMS as stand-alone treatment and in combination with psychotherapy. There is a break of 3-4 weeks between Phase 1 ending and Phase 2 beginning, so this period of time allows for rTMS to be conducted for patients willing to undergo this treatment.

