 - Incidence of serious and non-serious adverse events attributable to rTMS (eg: headache, scalp pain, facial pain, dizziness, tinnitus, light-headedness, syncope, seizure).
 - Montreal Cognitive Assessment (MOCA).

Procedures and Methods

After giving written, informed consent, subjects will undergo baseline assessment measures. Eligible subjects will be randomized to one of three treatment arms (high or low frequency rTMS, or sham rTMS). Concealment of allocation will be accomplished using a computerized randomization program that reveals treatment allocation only after the unique subject identifier is entered. The randomization codes will be available on a 24-hour basis in the (unlikely) event that the blind needs to be broken for clinical reasons. The subject will be blind to treatment condition because they will be unaware of the rTMS frequencies or sham condition used in the study. The rTMS nurse will be unblinded, but the

evaluator for clinician-rated assessments will be blind to treatment conditions. The rTMS nurse will not interact with the evaluator, and should any unblinding occur, the evaluator will be replaced.

The secondary outcome measures will be repeated weekly after rTMS session number 5 and 10 (or at termination, for early withdrawals). Adverse events and severity (mild, moderate, severe) will be recorded at each session. Serious adverse events will be defined according to standard Health Canada definitions as those which: a) result in death; b) are life threatening; c) are severely or permanently disabling; d) require inpatient hospitalization; e) result in an incidence of cancer; f) result in a drug overdose or reaction after drug withdrawal. All subjects who withdraw from the study will be asked to state a reason for withdrawal. The outcome measures will also be repeated after completion of the Phase 2 group psychotherapy program (about 10 weeks following completion of the rTMS).

The blind evaluator(s) will receive standardized training to establish inter-rater reliability using videotaped interviews. Reliability of outcome assessment will also be enhanced by using structured interview guides for the HAMD and CAPS.

Interventions (rTMS Stimulation)

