All randomized subjects will be included in the analysis based on intent-to-treat. Missing data will be imputed using last observation carried forward (LOCF). The pre-specified primary efficacy endpoint is the adjusted mean change from baseline to endpoint (2 weeks) on the PTSD Check List using LOCF. All comparisons will be analyzed using ANCOVA adjusting for baseline value. The secondary outcomes will also be analyzed using a similar analysis, when appropriate. Post hoc analyses will also rTMS & PTSD Protocol V3.0 6

examine observed case data. Categorical data (such as proportions of the sample with adverse events) will be analyzed using chi-square tests or Fisher's test where cell sizes warrant.

Reference List

- (1) APA. American Psychologic Association. Diagnostic and statistical manual of mental disorders . 4 ed. Washington, DC: APA; 1994.

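### LOCF is not limited to the 2-week endpoint, so scores taken before Phase 2 can enter the follow-up comparison and make a faded rTMS effect look partly retained

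*Combined protocol and SAP*

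**What the plan says.** The Data Analysis section of the combined protocol and SAP sets one missing-data rule: "Missing data will be imputed using last observation carried forward (LOCF". The sentence before it reads "All randomized subjects will be included in the analysis based on intent-to-treat". LOCF is named a second time for the primary endpoint: "The pre-specified primary efficacy endpoint is the adjusted mean change from baseline to endpoint (2 weeks) on the PTSD Check List using LOCF". Nothing there confines the general rule to that endpoint, and the model is also stated generally: "All comparisons will be analyzed using ANCOVA adjusting for baseline value". Observed cases are to be examined as well, but post hoc and with no visit named.

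Research Design schedules the outcome measures at baseline, week 1, week 2 and after Phase 2 of the group programme. Procedures and Methods confirms the last of these: "The outcome measures will also be repeated after completion of the Phase 2 group psychotherapy program", about 10 weeks after rTMS ends. No visit lies between week 2 and that reading, and rTMS is given before Phase 2 begins.

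The introduction says of the programme that patients completing Phase 1 improve very little, "but Phase 2 can have a greater impact". It also presents the longer-term and combined effects of rTMS and psychotherapy as an opportunity the study offers.

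**The concern.** LOCF at follow-up assumes that a subject's score does not move between week 2 and the end of Phase 2. The plan's own introduction gives two reasons to doubt this. Phase 2 is expected to move scores. The cited evidence on how long an rTMS effect lasts is also mixed. Of two small uncontrolled studies it says "Both studies showed improvement in core PTSD symptoms, but the effects were transient", whereas two sham-controlled trials are reported as showing benefit two to three months after treatment.

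Durability is therefore an open question, and the post-Phase 2 reading is the only one in the trial that addresses it. A rule that fills missing follow-up scores with week 2 scores pulls the follow-up contrast toward the week 2 contrast, and so partly presumes the answer. The pull works both ways: a contrast that shrank is overstated, and one that grew during Phase 2 is understated. If the arms lose different numbers of subjects, the Phase 2 improvement itself is credited unequally.

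**Working it through.** **Inputs from the plan.** d = 1.4, alpha 0.05, power 80% and nine subjects per condition (Sample Size); visits at weeks 1 and 2 and after Phase 2 (Research Design).

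**The plan's own figure.** With a two-sided normal approximation, n = 2 × (1.960 + 0.842)² / 1.4² = 15.70 / 1.96 = 8.01, rounded up to 9 per condition. This matches the plan. A two-sided t-test has 79.6% power at nine per arm. The sample size is not in question; 1.4 is used below only as the week 2 contrast.

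**Inputs assumed.** The plan gives no loss rate, no rate of fading and no size for the Phase 2 gain. Loss after week 2 is varied over 1, 2 and 3 of 9 per arm and taken as unrelated to outcome. Fading is complete, half or none. The Phase 2 gain, where it matters, is 0.5 to 1.0 SD and common to the arms.

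**Formula.** Work in SD units of improvement. For the two arms compared, A and B, let d2 be the week 2 contrast, dF the true follow-up contrast, g the common Phase 2 gain, and mA and mB the shares lost after week 2.

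- LOCF mean in A: (1 − mA)(dF + g) + mA × d2
- LOCF mean in B: (1 − mB) × g
- LOCF contrast: (1 − mA) × dF + mA × d2 − g × (mA − mB)
- Bias: mA × (d2 − dF) − g × (mA − mB)

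With equal loss p the last term vanishes, and the contrast is (1 − p) × dF + p × d2.

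**Equal loss, d2 = 1.4.**

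| Lost per arm | Complete fading (dF = 0) | Half fading (dF = 0.7) | No fading (dF = 1.4) |
|---|---|---|---|
| 1 of 9 | 1/9 × 1.4 = 0.16 | 1/9 × 0.7 = 0.08 | 0 |
| 2 of 9 | 2/9 × 1.4 = 0.31 | 2/9 × 0.7 = 0.16 | 0 |
| 3 of 9 | 3/9 × 1.4 = 0.47 | 3/9 × 0.7 = 0.23 | 0 |

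Entries are biases in SD. In simulations with nine per arm and complete fading, the follow-up test rejected in about 5-6%, 7-8% and 10-13% of trials at 1, 2 and 3 of 9 lost. With observed data it rejected in about 5%. The ranges reflect different simulation set-ups, including assumed within-subject correlations of 0.6 and 0.7.

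**A contrast that grows.** With dF = 1.8 and 20% lost per arm, LOCF gives 0.8 × 1.8 + 0.2 × 1.4 = 1.72, an understatement.

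**Unequal loss, g = 0.5 to 1.0.**

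- Complete fading, A loses 1 and B loses 3: 1/9 × 1.4 + 2/9 × g = 0.27 to 0.38 SD.
- Complete fading, A loses 3 and B loses 1: 3/9 × 1.4 − 2/9 × g = 0.36 down to 0.24 SD.
- No rTMS effect at any time: 2/9 × g = 0.11 to 0.22 SD against the arm that loses more.

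**The case against.** Several points on the other side are sound.

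- **The follow-up contrast is not a named endpoint.** The plan writes out one endpoint, at week 2, and repeats LOCF there. One could read the general sentence as meant only for it. But the sentence carries no such limit, all randomized subjects are kept, all comparisons share one model, and no other missing-data rule exists for follow-up.
- **Observed cases will be examined.** Under loss unrelated to outcome, that analysis is unbiased at follow-up. It would be wrong to infer that the plan offers nothing but LOCF. The check is only partial, because it is labelled post hoc and not tied to the follow-up reading.
- **Complete fading is the worst case.** The studies with transient effects were uncontrolled, one with ten patients given a single session and one with two patients. The two controlled trials reported lasting benefit. If that holds here, the bias under equal loss is zero.
- **Loss may be small.** Earlier studies are described as having little dropout, patients are expected to finish the 18-week programme, and the PCL-C is collected there routinely. At 1 of 9 lost per arm, the false-positive rate is close to nominal. The earlier studies, however, do not speak to attendance after a further 10-week group programme.
- **The direction is not certain.** With half fading and 3 versus 1 of 9 lost, a Phase 2 gain above (3/9 × 0.7) / (2/9) = 1.05 SD would reverse the bias. That is no argument for keeping LOCF.

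**Conclusion.** As written, the LOCF rule reaches the post-Phase 2 reading and puts pre-Phase 2 scores into it. The concern holds at the level of a change that should be made, not one on which the trial's main conclusion depends.

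A reader might infer that a faded effect would look durable. The arithmetic does not support that. Under equal loss, the share of the lost effect that reappears equals the share of subjects missing. At 2 of 9 lost, 1.4 SD that has vanished shows up as 0.31 SD and is non-significant about 92% of the time. A faded effect can look partly retained, no more. A reader might also infer that the primary result is compromised. It is not: the week 2 endpoint, the primary hypothesis and the sample size are untouched by this point.

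The figures rest on d = 1.4 at week 2 and on assumed loss, fading and Phase 2 gain, none of which the plan states. The formula and the lack of a visit limit do not depend on those assumptions.

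**What to change.** In Data Analysis, limit LOCF to the week 2 endpoint and pre-specify that the post-Phase 2 reading is analysed without it.

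- **Preferred:** a likelihood-based repeated-measures model with change at week 1, week 2 and follow-up as outcomes; arm, visit, arm-by-visit, baseline and baseline-by-visit as terms; and an unstructured covariance. Take the between-arm contrasts at follow-up from it. Three visits need six covariance parameters, to be estimated from about 27 subjects, so name a small-sample degrees-of-freedom correction such as Kenward-Roger. Without one, normal-reference tests rejected in 6.3-7.1% of simulated trials.
- **Minimum:** a pre-specified baseline-adjusted ANCOVA on observed follow-up scores, which moves the existing post hoc check into the plan for this visit.

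In either case, report the number of observed follow-up scores per arm.

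The cost is a sentence or two. No new data are needed, and neither the sample size nor the primary analysis changes. The downside is wider confidence intervals at follow-up when subjects are lost. Both options still assume something about why scores are missing, which is why the counts per arm should be shown.

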The motor threshold is determined during the first session by applying TMS over the motor cortex in order to get the minimal level of stimulus intensity from the device which will create a contraction in the contralateral abductor pollicis brevis muscle of the thumb. The DLPFC will be targeted by measuring 6 cm anterior to this motor cortex landmark, along the sagittal plane, as the patient will be wearing a swimmer's cap. The intensity of the stimulus is set by going 100-120% of the intensity which determined motor threshold. rTMS therapy over the right DLPFC will be given on 5 consecutive days every week for two weeks for a total of 10 therapy sessions using a Magstim Super Rapid2 (Magstim Company Ltd., Carmarthenshire, Wales, UK) with a Rapid-2 Air Film Coil.

Subjects will receive either active rTMS to the right side at 1 Hz or at 10 Hz, or sham treatment for 37.5 minutes per session. The stimulus parameters that will be chosen for treating subjects will be similar to the parameters currently used at our clinic to stimulate patients with depression. A clinic nurse will always be present to deliver the treatment, and a supervising rTMS psychiatrist will oversee the appropriate placement and intensity of the coil, as well as responding to any adverse event which may arise. Each subject is given appropriate ear protection due to the intensity of the sound from each treatment pulse delivered by the device. Subjects who experience some initial discomfort during the session, such scalp or facial irritation, will prompt trying a different orientation of the coil at the same DLPFC site, which will usually relieve the discomfort. Subjects may leave immediately on their own after the treatment is completed, and may even drive, unless a serious adverse event occurred.

SAMPLE SIZE

Based on the standardized effect size for the primary outcome, the PTSD Check List, as determined by the previous RCT (71;72) (d=1.4), and with alpha set to 0.05 and 80% power, we estimated a sample size of nine subjects/condition. Note that this effect size is regarded as a large effect and is clinically significant.

Data Analysis

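### Adverse events are graded at each of 10 sessions, but the only comparison named is any event per subject, so repeat events, severity and sessions attended go unused

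*Combined protocol and SAP*

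**What the plan says.** Under Secondary Outcomes, safety and tolerability are listed with this measure: "Incidence of serious and non-serious adverse events attributable to rTMS". The examples there run from headache and scalp pain to syncope and seizure. Procedures and Methods says how the data arise: "Adverse events and severity (mild, moderate, severe) will be recorded at each session". Interventions (rTMS Stimulation) fixes the exposure at five days a week for two weeks, "for a total of 10 therapy sessions".

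On analysis, the Data Analysis section has one relevant sentence: "Categorical data (such as proportions of the sample with adverse events) will be analyzed using chi-square tests", or by Fisher's test if the cell sizes call for it. It does not mention repeat events in one subject, severity grade, or the number of sessions attended. It also does not say whether the test is pairwise or across all three arms.

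The SAMPLE SIZE section sizes the trial on the PTSD Check List alone: "we estimated a sample size of nine subjects/condition". No adverse-event rate is given anywhere. The background describes adverse events as few and dropout in earlier trials as low. Procedures and Methods nevertheless allows for early withdrawals and asks each one for a reason.

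**The concern.** With full attendance each arm supplies 9 × 10 = 90 graded session records. The named analysis turns these into nine yes/no values. A subject with one mild headache counts the same as a subject with a moderate headache at every session. A subject who leaves after two sessions counts the same as one who completes ten.

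This matters most for the mild, recurring complaints that decide tolerability. If most subjects in each arm report scalp pain at least once, the proportions cannot separate 10 Hz, 1 Hz and sham, even when one arm has the complaint twice as often. If one arm also loses subjects early, its proportion falls because those subjects had fewer chances to report an event.

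**Working it through.** **The plan's own figure.** Inputs from SAMPLE SIZE: d = 1.4, "with alpha set to 0.05 and 80% power". Taking the test as two-sided, n per arm = 2(1.960 + 0.842)²/1.4² = 15.70/1.96 = 8.01, rounded up to 9. Power by the t distribution at nine per arm is 79.6%. The stated figure reproduces, but it concerns the PTSD Check List and implies nothing about adverse events.

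**Which test applies.** Suppose t of 18 subjects in a pairwise comparison have an event. The expected cell counts are t/2 and (18 − t)/2. Both reach 5 only if t ≥ 10 and t ≤ 8, which is impossible. Across three arms the condition is t ≥ 15 and t ≤ 12, also impossible. If the undefined cell-size rule means the usual threshold of 5, Fisher's test will always be used. Chi-square is shown as well because the plan names it.

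**What Fisher's test can detect at nine per arm.**
- 0/9 v 4/9: p = 2 × 126/3060 = 0.082.
- 0/9 v 5/9: p = 2 × 126/8568 = 0.029.
- By symmetry, 5/9 v 9/9 also gives 0.082. So once five of nine subjects in the less affected arm have had any event, no excess in the other arm can reach p < 0.05.

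**When the proportion saturates.** For per-session probability s and independent sessions, the risk of any event over 10 sessions is 1 − (1 − s)¹⁰:

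| s | 1% | 2% | 5% | 10% | 20% | 30% |
|---|---|---|---|---|---|---|
| Any event | 10% | 18% | 40% | 65% | 89% | 97% |

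Saturation therefore needs roughly 10-20% or more per session, and weak correlation within subject.

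**Power.** The table rests on 3,000 simulated trials per row (simulation standard error at most √(0.25/3000) = 0.9 points), with nine per arm, full attendance, beta-binomial session counts, pairwise comparison and two-sided 5%. With everyone attending all 10 sessions, ranking counts and ranking shares are the same thing. Rates and correlations are assumed.

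| Per-session rates | Correlation | Fisher, any event | Chi-square, any event | Rank test, session count |
|---|---|---|---|---|
| 20% v 40% | 0 | 0% | 1% | 76% |
| 20% v 40% | 0.1 | 2% | 9% | 50% |
| 20% v 40% | 0.3 | 11% | 25% | 31% |
| 20% v 40% | 0.5 | 13% | 23% | 22% |
| 10% v 30% | 0 | 13% | 31% | 87% |
| 10% v 30% | 0.3 | 27% | 41% | 44% |
| 5% v 15% | 0 | 28% | 43% | 54% |
| 5% v 15% | 0.3 | 16% | 29% | 26% |
| 2% v 6% | 0 | 13% | 26% | 22% |
| 2% v 6% | 0.3 | 2% | 7% | 7% |

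Repeat simulations of 20% v 40% at correlation 0.3 gave 29% to 33% for the rank test. With equal rates of 10%, false positives were about 2% for Fisher, 5.5-6.9% for uncorrected chi-square and 4-5% for the rank test, so chi-square's power is slightly flattered. Further runs with events concentrated early and with event-driven dropout never found the rank test on session share less powerful than Fisher; false positives were about 3-6%.

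**Sessions attended.** Take 10% per session in one arm, all completing: 1 − 0.9¹⁰ = 65% with any event. Take 15% in the other, with three of nine leaving after session 2 for unrelated reasons: (6 × 0.803 + 3 × 0.278)/9 = 63%. The arm with the 50% higher rate looks marginally better. Per session attended, its expected rate is (66 × 0.15)/66 = 15%, against 10%.

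**The case against.** The strongest objection is that saturation is assumed. The documents give no rate and describe adverse events as few; at 1%, 2% or 5% per session nothing saturates. This stands. A reader might infer that the proportion saturates as a matter of course and so leaves the safety comparison with almost no power. The documents do not support that. Power is low at unsaturated rates too: Fisher has 4% for 2% v 4% per session and 10% for 5% v 10%. The main cause is nine subjects per arm in a pilot that promises no powered safety test. Nor is power low for every contrast: 2% v 20% per session gives Fisher 84%.

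A session-level analysis does not rescue the comparison generally. For 2% v 4% per session with independent sessions, the rank test has about 8% power. With correlation 0.5 it gains nothing over chi-square even at 20% v 40%.

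The exposure argument also has limits. It needs events spread across sessions. The Interventions section expects some discomfort to be initial and usually relieved, so events may cluster early, and a subject who leaves because of an event is already counted. In that case session shares mislead the other way, because early leavers have high shares on small denominators.

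Finally, the proportion is offered only as an example of categorical data, and it matches an outcome worded as incidence. So the plan does not exclude other summaries. But it names none, which leaves the choice open until the data are seen.

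**Conclusion.** The point holds in limited form. The plan collects graded adverse-event data at each session and names only a subject-level yes/no comparison, leaving repeat events, severity and sessions attended without a specified use. The loss is large for common events that recur with weak within-subject correlation. It is small relative to Fisher, and absent relative to uncorrected chi-square, when events are rare or strongly correlated within subject. In those settings the sample size is the constraint and no choice of analysis removes it. The possible understatement in an arm with more early withdrawal is separate from power and depends on events being spread over sessions.

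The size of each effect rests on assumed rates and correlations. The absence of any stated use for grade, repetition or exposure does not. The change is worth making because it is nearly free, not because the safety comparison is otherwise invalid.

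**What to change.** In Data Analysis, keep subject-level incidence by arm with exact confidence intervals, and keep Fisher's test for rare or serious events. Then add, for common non-serious events:

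- For each subject, the share of attended sessions with the event, overall and restricted to moderate or severe grade.
- A comparison of arms by an exact rank or permutation test with the subject as the unit, stating whether it is pairwise or across three arms.
- The between-arm estimate with a 95% confidence interval that allows for clustering within subject.
- Presentation beside withdrawals by arm and reason, so that early leaving can be read with the shares.
- A label of exploratory.

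The cost is a few sentences and a little programming, with no new data, visits or staff. The drawbacks are a few extra exploratory tests and unstable shares for subjects who attend very few sessions; showing the number of sessions attended deals with the second in part.

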In Canada, there are no restrictions for the range of mental disorders that rTMS can be used for in treating patients, although MDD is the condition that is the most commonly treated. Based on reports in the literature, we anticipate that right sided rTMS is as safe and tolerable as left-sided rTMS. Therefore, we propose to conduct a study of rTMS in patients with PTSD who are starting the group psychotherapy program at VGH. Since previous research has shown a discrepancy between the efficacy of high versus low frequency rTMS on the symptoms of PTSD, we will examine the use of high (10 Hz) versus low (1 Hz) frequency rTMS delivered over the right DLFPC of patients suffering with PTSD symptoms unrelated to combat. Standardized evaluations will be done to assess for clinical improvements in the PTSD, depressive and anxiety symptom clusters, and for tolerability with monitoring of adverse events and dropout rates.

Primary Hypothesis

The primary hypothesis is that high frequency (10 Hz) rTMS over the right DLPFC will be superior to low frequency (1 Hz) in reducing scores as measured by the PTSD Check List.

Research Method

Subject Recruitment

Subjects will be recruited from the PTSD treatment program conducted at the VGH Outpatient Psychiatry Program (OPP). Mid-way during the Phase 1 of the group psychoeducational program, patients will be approached regarding their willingness to participate in the study. Those subjects expressing interest will receive a description of the study along with an informed consent form that the client can sign if s/he chooses to participate. Should the patient agree to participate, a screening interview will be administered to determine if s/he meets the inclusion / exclusion criteria.

Inclusion criteria: (1) primary diagnosis of PTSD as determined by a structured interview (Mini International Neuropsychiatric Interview, MINI (68)); (2) no change in psychotropic medications within 4 weeks before the start of rTMS; (3) age greater than 19 years and less than 70 years; and (4) competent to give informed consent.

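### Adverse events: at nine per arm a chi-square or Fisher test says little, so the planned comparison should be counts with exact intervals, and p>0.05 should not be read as similar tolerability

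*Combined protocol and SAP*

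**What the plan says.** Under Secondary Outcomes, the adverse events, safety and tolerability item begins with "Incidence of serious and non-serious adverse events attributable to rTMS" and gives eight example events. The aims, set out just before Primary Hypothesis, say standardized evaluations will be made of symptoms and "for tolerability with monitoring of adverse events and dropout rates". Procedures and Methods adds that events are graded for severity at every session and that subjects who withdraw are asked for a reason.

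Data Analysis has one sentence on how this is to be analysed: "Categorical data (such as proportions of the sample with adverse events) will be analyzed using chi-square tests", or Fisher's test when cell sizes call for it. It does not define that condition, does not say whether arms are compared in pairs or all three together, and mentions no confidence interval. No analysis is named for withdrawal unless that sentence is taken to cover it.

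The arm size comes from the efficacy calculation under SAMPLE SIZE: "we estimated a sample size of nine subjects/condition". With three arms that is 27 subjects. Research Design calls the trial a pilot.

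**The concern.** Incidence is a quantity to be estimated, but the method attached to it is a test of difference. With nine subjects per arm such a test detects only very large differences. If the safety result is reported as a p-value, a non-significant one is easily taken to mean that the arms were tolerated alike, when the data exclude very little. What a later, larger trial would need from this pilot is the event and withdrawal rates and their uncertainty, and the plan does not promise the second of these.

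**Working it through.** **Inputs.** From SAMPLE SIZE: nine per condition, alpha 0.05, 80% power, d=1.4 on the PTSD Check List. From Procedures and Methods: three arms. Assumed, because the documents do not say: two-sided tests, 0.05 applied to adverse events as well, nine analysed in each arm. The true event rates below are illustrative, since the documents give none.

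**The plan's own figure.** n = 2(1.96 + 0.84)²/1.4² = 8.01, rounded up to 9 per arm. The t-test version gives 9.08 (power 79.6% at nine). The stated nine is reproduced, but it was set for the PTSD Check List alone. No power or detectable difference is given for adverse events.

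**Which test applies.** Let k be the total number of subjects with the event.
- Two arms of nine: the expected counts are k/2 and 9 − k/2. They sum to 9, so the smaller is at most 4.5.
- Three arms of nine: they are k/3 and 9 − k/3. The smaller is at most 4.33 (k = 13 or 14).

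If the protocol's condition means the usual rule of 5, Fisher's test (or its three-arm extension) applies to every table.

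**Gap needed for p<0.05.** A pairwise table with a and b events has probability C(9,a)·C(9,b)/C(18,a+b). The two-sided p-value sums this over all tables no more probable than the one observed.
- 0 v 4: 2 × 126/3060 = 0.082, not significant.
- 0 v 5: 2 × 126/8568 = 0.029.
- 1 v 6: 0.0498.
- 2 v 7: 0.057, not significant; 2 v 8: 0.015.
- 3 v 8: 0.0498.
- 4 v 9: 0.029.

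So the pairwise minimum is five subjects, and six when the lower arm has two events. For three arms, 0/0/4 gives 3 × 126/17550 = 0.0215. Enumerating all 9/9/9 tables shows that four is the smallest significant gap.

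**Power.** This is the sum of the binomial probabilities of all significant tables. For pairwise Fisher at 9 v 9:

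| Assumed true rates | Power |
|---|---|
| 10% v 40% | 14% |
| 10% v 50% | 30% |
| 10% v 60% | 49% |
| 10% v 80% | 83% |

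The three-arm exact test has 22% power when one arm is at 40% and two at 10%, and 21% when two are at 40% and one at 10%. Both active arms together (18) against sham (9) give 22%, 47% and 72% for 10% in sham against 40%, 50% and 60%.

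**What an interval would show.**
- No events in one arm: the exact upper 95% limit is 1 − 0.025^(1/9) = 33.6%. For 0/18 it is 1 − 0.025^(1/18) = 18.5%.
- Other exact intervals at nine: 1/9, 0.3% to 48.3%; 2/9, 2.8% to 60.0%; 4/9, 13.7% to 78.8%.
- Difference between arms with 2/9 each: the test gives p = 1. The Wilson limits for 2/9 are 0.063 and 0.547, so the Newcombe interval is ±√[(0.222 − 0.063)² + (0.547 − 0.222)²], about −36 to +36 percentage points.
- 4/9 against 2/9: about −19 to +55 points.

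**The case against.** The strongest reply is that this is a pilot sized for efficacy. It states no tolerability hypothesis, margin or equivalence claim, and nowhere says that a non-significant test will be read as similarity. Intervals add no information, since 0/9 remains compatible with a true rate of about 34% however it is reported. This stands as far as it goes: the imprecision comes from the sample size, and the fix does not remove it. What the fix does is put the imprecision in the report, where p = 1 for 2/9 against 2/9 would hide it.

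Several stronger readings might be inferred, and the documents do not support them:
- *Any test the plan allows needs a gap of five.* That is true of two-sided pairwise Fisher and of the Yates-corrected chi-square. Uncorrected chi-square reaches p<0.05 at 0 v 4 (p=0.023), and the three-arm exact test does so at 0/0/4. The protocol does not say which comparison it means.
- *The result will be non-significant whatever the true rates.* Power is 83% at 10% v 80%, so very large differences would be seen.
- *The plan offers no estimate.* Its analysis sentence already refers to proportions and its outcome is an incidence. What is absent is an interval.
- *The plan cannot answer its tolerability question.* It poses no formal one, and it collects severity, serious events, cognitive scores and reasons for withdrawal, all of which can be described without a test.
- *Failing to combine the active arms is an error.* The primary hypothesis contrasts the two frequencies, so separate reporting is natural. Combining them is an option.

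**Conclusion.** The point holds as an inexpensive improvement to a secondary outcome. The plan names only a significance test for adverse event proportions and no interval. Under the usual expected-count rule that test is Fisher's, which at nine per arm needs a gap of five subjects pairwise or four across three arms. A rise from 10% to 40% would be missed about 86% of the time pairwise and about 78% of the time by the three-arm exact test. Uncorrected pairwise chi-square, poorly suited to such small counts, would still miss it about 69% of the time (power 31%). On any of these readings, p>0.05 cannot carry a conclusion of similar tolerability.

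This rests on two-sided 0.05, nine analysed per arm, and event rates chosen for illustration. The gap thresholds do not depend on the assumed rates; the power figures do.

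**What to change.** In Data Analysis, make estimation the adverse event analysis:

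- For each arm, give the number and proportion of subjects with any event, any serious event, each named event, and withdrawal, with exact (Clopper-Pearson) 95% intervals.
- For any event and for withdrawal only, give the risk differences 10 Hz minus 1 Hz and active minus sham, with a named small-sample 95% interval such as Newcombe's. State in advance whether active means each frequency or both together.
- State whether Fisher's tests are pairwise or three-arm, label their p-values descriptive, and say that similar tolerability will not be inferred from p>0.05.
- Optionally, show a combined active row (n=18) beside the separate arms.

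The cost is a few sentences and a longer safety table, with no new data, subjects or procedures. With the eight example events there are 8 + 3 = 11 rows, so 33 exact intervals over three arms, or 44 with the combined row. Limiting the risk differences to two outcomes keeps those to a handful. The intervals will be wide, and the combined row averages two frequencies, which is why it should not replace the separate arms.
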